4.2.2. Adherence to Study Drug

4.2.2.1. On-Treatment Adherence for TAF (Cohort 1 Only)

The level of on-treatment adherence to TAF will be determined by the total amount of study drug administered relative to the total amount of study drug expected to be administered during a participant's actual on-treatment period (ie, by Week 36) based on the study drug regimen.

The level of on-treatment adherence will be expressed as a percentage using the following formula:

Adherence (%) =
$$\left(\frac{\text{Total number of tablets taken}}{\text{Total number of tablets prescribed}}\right) \times 100$$

$$= \frac{\sum \text{No. of tablets taken at each dispensing period [1]}}{\sum \text{No. of tablets prescribed at each dispensing period [2]}} \times 100$$

- [1] Number of tablets taken during a distinct dispensing period for TAF is calculated as the minimum of (a) the daily number of tablets prescribed for the study drug multiplied by the **duration of treatment** at the dispensing period of the same dispensing date, and (b) the number of tablets taken for the study drug (number of tablets dispensed minus the number of tablets returned). Total number of tablets taken is determined by summing the number of tablets taken from all evaluable dispensing periods.
- [2] Number of tablets prescribed at a distinct dispensing period for TAF is calculated as the daily number of tablets prescribed for the study drug multiplied by the **duration of treatment** at the dispensing period of the same dispensing date. Total number of tablets prescribed is determined by summing the number of tablets prescribed from all evaluable dispensing periods.

The duration of treatment (in days) at a dispensing period for TAF is calculated as the minimum of (a) the last returned date of the same dispensing period for the study drug, (b) date of premature discontinuation of the study drug, and (c) next dispensing date of the study drug, minus dispensing date of the study drug.

The **next dispensing date** is the following dispensing date of the study drug regardless of the bottle return date.

For a record where the number of tablets returned was missing (with "Yes" answered for "Was bottle returned?" question), then this record will be excluded from both denominator and numerator calculation. If the number of tablets dispensed was missing or any study drug bottle was not returned or the bottle return status was unknown for the same dispensing date, then all records for the same dispensing date for that study drug will be excluded from both denominator and numerator calculation.

Adherence up to end of treatment will be calculated for each participant in Cohort 1.

The number and percentage of participants who return at least 1 bottle and have calculable adherence during the study, descriptive statistics (sample size, mean, SD, median, Q1, Q3, minimum, and maximum) for adherence up to end of treatment visit (ie, Week 36) along with the number and percentage of participants belonging to adherence categories (eg, < 80%, $\ge 80\%$ to < 90%, $\ge 90\%$ to < 95%, $\ge 95\%$) will be summarized for Cohort 1 participants based on the Safety Analysis Set.

4.2.2.2. On-Treatment Adherence for SLGN

The level of on-treatment adherence to the study drug regimen will be determined by the total amount of study drug administered relative to the total amount of study drug expected to be administered during a participant's actual on-treatment period based on the study drug regimen.

The level of on-treatment adherence will be expressed as a percentage using the following formula:

Adherence (%)
$$= \left(\frac{\text{Total Amount of SLGN Administered [1]}}{\text{Total Amount of SLGN Expected to be Administered on Treatment [2]}}\right) \times 100$$

- [1] The total amount of SLGN administered to a participant will be determined by Σ No. of tablets dispensed Σ No. of tablets returned based on the study drug accountability CRF.
- [2] The total amount of SLGN expected to be Administered on treatment is determined as follows:
- a For participants who completed SLGN, the amount of SLGN expected to be administered will be the 6×8 tablets;
- b For participants who did not complete SLGN, the total amount of SLGN expected to be administered is the sum of number of tablets expected to be taken at each dispensing period, which is calculated as the number of on-treatment weeks on or before the last dosing date for SLGN multiplied by the number of tablets expected to be taken at each dispensing period (ie, 8 tablets). If there are more than 6 dispensing visits for a participant, 6 visits will be used for calculation.

Descriptive statistics for the level of on-treatment adherence with the number and percentage of participants belonging to adherence categories (< 95%, $\ge 95\%$) will be provided by cohort (and by treatment group for Cohort 2) for the Safety Analysis Set.

4.2.2.3. On-treatment Adherence for VIR-2218 (Cohort 1 and Cohort 2 Group A only)

The level of on-treatment adherence to VIR-2218 will be determined by the total amount of VIR-2218 administered relative to the total amount of VIR-2218 expected to be administered during a participant's actual on-treatment period based on the study drug regimen.

The level of on-treatment adherence will be expressed as a percentage using the following formula:

Adherence (%)
$$= \left(\frac{\text{Total Amount of VIR} - 2218 \text{ Administered [1]}}{\text{Total Amount of VIR} - 2218 \text{ Expected to be Administered on Treatment [2]}}\right) \times 100$$

- [1] The total amount of VIR-2218 administered to a participant will be determined by $(\sum No. \text{ of vials dispensed}) (\sum No. \text{ of vials returned})$ based on the drug accountability CRF
- [2] The total amount of VIR-2218 expected to be administered on treatment is determined as follows:
- a For participants who completed VIR-2218, the amount of VIR-2218 expected to be administered will be the 6 × 2 vials;
- b For participants who did not complete VIR-2218, the number of VIR-2218 expected to be administered is determined by the last on-treatment visit. For example, if the last on-treatment visit is Week 12, the number of VIR-2218 expected to be administered for this participant will be 4 × 2 vials.

Descriptive statistics for the level of on-treatment adherence with the number and percentage of participants belonging to adherence categories (< 100%, 100%) will be provided by cohort for the Safety Analysis Set.

4.2.2.4. On-Treatment Adherence for Nivolumab

The level of on-treatment adherence to nivolumab will be determined by the total amount of study drug administered relative to the total amount of study drug expected to be administered during a participant's actual on-treatment period based on the study drug regimen.

The level of on-treatment adherence will be expressed as a percentage using the following formula:

Adherence (%)
$$= \left(\frac{\text{Total No. of Nivolumab Administered [1]}}{\text{Total No. of Nivolumab Expected to be Administered on Treatment [2]}}\right) \times 100$$

- [1] The total number of nivolumab administered to a participant will be determined by the number of doses administered based on the study drug administration CRF.
- [2] The total number of nivolumab expected to be administered on treatment is determined as follows:
- For participants who completed nivolumab, the number of nivolumab expected to be administered will be set to 6;
- b For participants who did not complete nivolumab, the number of nivolumab expected to be administered is determined by the last administration visit (for example, for a participant in Cohort 1 and Cohort 2 Group A, if the last administration visit is Week 16, the number of nivolumab expected to be administered will be 2; for a participant in Cohort 2 Group B, if the last administration visit is Week 16, the number of nivolumab expected to be administered will be 5).

For participants who never initiate nivolumab, adherence will not be calculated.

Descriptive statistics for the level of on-treatment adherence with the number and percentage of participants belonging to adherence categories (< 50%, 50% to < 75%, 75% to < 100%, 100%) will be provided by cohort (and by treatment group for Cohort 2) for the Safety Analysis Set.

4.3. Protocol Deviations

Participants who did not meet the eligibility criteria for study entry but enrolled in the study, will be summarized regardless of whether they were exempted by the sponsor or not. The summary will present the number and percentage of participants who did not meet at least 1 eligibility criterion and the number of participants who did not meet specific criteria by treatment group based on the All Enrolled/Randomized Analysis Set. A by-participant listing will be provided for those participants who did not meet at least 1 eligibility (inclusion or exclusion) criterion. The listing will present the eligibility criterion (or criteria if more than 1 deviation) that participants did not meet and related comments, if collected.

Protocol deviations occurring after participants entered the study are documented during routine monitoring. The number and percentage of participants with important protocol deviations (e.g., at least 1, with 1, 2, 3 or more important protocol deviations), and the total number of important protocol deviations by deviation category (e.g., eligibility criteria, informed consent) will be summarized by cohort (and by treatment group for Cohort 2) for the Enrolled/Randomized Analysis Set. A by-participant listing will be provided for those participants with important protocol deviation.

4.4. Assessment of COVID-19 Impact

This study was ongoing during the novel coronavirus (COVID-19) pandemic which has an impact on the study conduct. Some participants were unable to attend onsite visits due to shelter in place guidelines, site closures, or other reasons. This section describes how special situations due to COVID-19 will be handled in the analysis. Please refer to Appendix 3 for data collection and determination of COVID-19 Data.

4.4.1. Study Drug or Study Discontinuation Due to COVID-19

A by-participant listing of reasons for premature study drug or study discontinuation due to COVID-19 will be provided if applicable.

4.4.2. Protocol Deviations Due to COVID-19

A by-participant listing will be provided for participants with important protocol deviations related to COVID-19 if applicable. A separate listing will be provided for participants with non-important protocol deviations related to COVID-19 if applicable.

4.4.3. Missed and Virtual Visits due to COVID-19

A by-participant listing of participants with missed or virtual visits due to COVID-19 will be provided by participant ID number in ascending order.

Missed or virtual visits due to COVID-19 will be collected on the visit date CRF page.

4.4.4. Adverse Events Due to COVID-19

AEs of COVID-19 will be included in analyses of AEs if applicable, which will be determined through MedDRA COVID-19 SMQ narrow search. A by-participant listing of AEs of COVID-19 will be provided if applicable.

4.4.5. Overall Assessment of COVID-19 Pandemic Impact

For participants affected by COVID-19 infection and/or pandemic while participating in the study, a listing of the following individual COVID-19 related outcome categories will be provided:

- Death due to COVID-19
- Adverse event of COVID-19, as determined by COVID-19 SMQ narrow search
- Specific adverse event directly associated with the pathogen causing COVID-19, as determined by MST
- Hospitalization (using data from AE eCRF) due to adverse event of COVID-19 as defined above
- Study drug discontinuation due to COVID-19
- Study discontinuation due to COVID-19
- Missed visits due to COVID-19
- Missed key assessments due to COVID-19 (Key assessments are the assessments contributing to primary endpoint, ie, FU Week 24 assessments related to qualitative HBsAg and quantitative HBV DNA)

In addition, composite broad COVID-19 impact indicator will be derived based on the following individual categories defined above: death, adverse event, hospitalization, study drug discontinuation, study discontinuation, missed visits, and missed key assessments. Composite specific COVID-19 impact indicator will be derived based on death and specific adverse event.

5. BASELINE CHARACTERISTICS

5.1. Demographics and Baseline Characteristics

Participant demographic variables (ie, age, sex, race, and ethnicity) and baseline characteristics (body weight [in kg], height [in cm], body mass index [BMI; in kg/m²]) will be displayed by cohort and study overall using descriptive statistics for continuous variables and using number and percentage of participants for categorical variables. Within Cohort 2, the summary will be presented by treatment group (Group A or Group B) and HBsAg category (HBsAg > 3 and \leq 3 log₁₀ IU/mL). The summary of demographic data will be provided for the Safety Analysis Set.

A by-participant demographic listing, including the informed consent date, and stratification group (for Cohort 2 only), will be provided by cohort (and by treatment group for Cohort 2), and participant ID number in ascending order.

5.2. Other Baseline Characteristics

Other baseline characteristics include:

- HBsAg (log₁₀ IU/mL) as a continuous variable
- HBsAg ($\log_{10} IU/mL$) as categories (< 2, 2 to < 3, 3 to < 4, \geq 4)
- HBV DNA (log₁₀ IU/mL) as a continuous variable
- HBV DNA (log_{10} IU/mL) as categories (< LLOQ, LLOQ to < 3.3, 3.3 to < 4.3, \geq 4.3)
- HBeAg/HBeAb status (negative, positive)
- HBV genotype
- ALT (U/L) as a continuous variable
- ALT level as categories based on central laboratory normal range (≤ upper limit of normal [ULN], > ULN to 5 × ULN, > 5 × ULN to 10 × ULN, > 10 × ULN)
- FibroTest Score as a continuous variable
- Fibrosis Stage by FibroTest Score as categories (0.00 to 0.48, 0.49 to 0.74, 0.75 to 1.00)
- APRI $(\leq 1, \geq 1)$
- Current oral nucleoside/nucleotide treatment

- Previous interferon experience to treat HBV (yes, no)
- Duration of being HBV positive (in years) as a continuous variable
- Mode of HBV infection
- Estimated glomerular filtration rate using the Cockcroft-Gault equation (eGFR_{CG}) (mL/min), which will be calculated as follows:

```
eGFRCG (mL/min) = [(140 - age [years]) \times weight (kg) \times (0.85 if female)] / (serum creatinine [mg/dL] \times 72), where weight is actual body weight in kilograms
```

These baseline characteristics will be summarized by cohort and study overall using descriptive statistics for continuous variables and using number and percentage of participants for categorical variables. Within Cohort 2, the summary will be presented by treatment group (Group A or Group B) and HBsAg category (HBsAg > 3 and \leq 3 log₁₀ IU/mL). The summary of these baseline characteristics will be provided for the Safety Analysis Set. No formal statistical testing is planned.

A by-participant listing of other baseline characteristics, including HBsAg category for Cohort 2, will be provided by cohort (and by treatment group for Cohort 2), and participant ID number in ascending order.

5.3. Medical History

General medical history data will be collected at screening and listed only.

6. EFFICACY ANALYSES

6.1. Primary Efficacy Endpoint

6.1.1. Definitions of Primary Efficacy Endpoint

The primary efficacy endpoint of this study is defined as the proportion of participants who achieve functional cure, defined as HBsAg loss and HBV DNA < LLOQ at FU Week 24.

6.1.2. Statistical Hypothesis for Primary Efficacy Endpoint

No statistical hypothesis testing will be performed.

6.1.3. Analysis of Primary Efficacy Endpoint

The primary efficacy analysis will be performed for the FAS after the last participant has completed FU Week 24 assessments or prematurely discontinued study drug.

Analysis for Cohort 1:

The point estimates and the 2-sided 95% exact confidence interval (CI) of the primary efficacy endpoint will be provided. The CIs of the proportion point estimates will be constructed based on the Clopper-Pearson method {Clopper 1934}.

Analysis for Cohort 2:

To compare Group A and Group B for HBsAg categories(> 3 and \leq 3 log₁₀ IU/mL) separately, point estimates and the 2-sided 95% exact confidence intervals (CIs) of the primary efficacy endpoint will be provided based on the Clopper-Pearson method {Clopper 1934} by HBsAg status and overall for each treatment group.

In addition, point estimates and the 2-sided 95% exact CIs of the proportion difference between Group A and Group B will be displayed separately by HBsAg category for each treatment group. CIs for the proportion differences will be constructed based on the standardized statistic and inverting two 1-sided tests {Chan 1999}.

To compare Group A and Group B for pooled HBsAg > 3 and \leq 3 log₁₀ IU/mL participants, the proportion differences and the corresponding 95% CIs will be calculated using the stratum-adjusted Mantel-Haenszel (MH) method {Koch 1989}, stratified by HBsAg category(> 3 and \leq 3 log₁₀ IU/mL), as follows:

$$P_1-P_2\pm Z_{(1-\alpha/2)}\times SE(P_1-P_2)$$

where

- $(P_1 P_2) = \frac{\sum w_h d_h}{\sum w_h}$ is the stratum-adjusted MH proportion difference, where $d_h = P_{1h} P_{1h}$ is the proportion difference of group 1 and group 2 in stratum h (h = 1 and 2).
- $w_h = \frac{n_{1h}n_{2h}}{n_{1h} + n_{2h}}$ is the weight based on the harmonic mean of sample size for stratum h, where n_{1h} and n_{2h} are the sample sizes of groups 1 and 2 in stratum h.
- SE(P₁ P₂) = $\sqrt{\frac{\sum w_h^2 \left[\frac{p_{1h}(1-p_{1h}^*)}{n_{1h}-1} + \frac{p_{2h}^*(1-p_2^*)}{n_{2h}-1}\right]}{(\sum w_h^2)}}$, where $p_{1h}^* = \frac{m_{1h}+0.5}{n_{1h}+1}$ and $p_{2h}^* = \frac{m_{2h}+0.5}{n_{2h}+1}$, and m_{1h} and m_{2h} are the number of participants who achieve the primary efficacy endpoint in groups 1 and 2 respectively in stratum h.
- Groups 1 and 2 (in the equations above) represent Group A and Group B from Cohort 2 respectively.
- $\alpha = 0.05$ for this study.
- $Z_{(1-\alpha/2)} = Z_{0.975} = 1.96$ is the 97.5th percentile of the normal distribution.

If the computed lower confidence bound is less than -1, the lower bound is defined as -1. If the computed upper confidence bound is greater than 1, then the upper bound is defined as 1.

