1. INTRODUCTION

This statistical analysis plan (SAP) describes the statistical analysis methods and data presentations to be used in tables, figures, and listings (TFLs) in the clinical study report (CSR) for Study GS-US-465-4439. This SAP is based on the study protocol amendment 2 dated 12 April 2023 and the electronic case report form (eCRF). The SAP will be finalized before the Primary Analysis at Follow-up (FU) Week 24 when all participants complete Follow-Up (FU) Week 24 or early terminated from the study prior to FU Week 24, and will be used for both Primary Analysis and Final Analysis. Any changes made after the finalization of the SAP will be documented in the CSR.

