1.2.1. Changes to Study Design

Nivolumab dosing was stopped by Gilead as part of benefit-risk assessment based on emerging safety data from this study, other studies evaluating anti-PD-1/PD-L1 mAbs, and pertinent patient and prescriber insights {Cohen C. 2020}. As the study had completed enrollment and all participants were undergoing study treatment when the decision was made to stop nivolumab administration, the following measures were implemented:

- Stopped further nivolumab administration for all study participants across all cohorts
- Continued treatment with VIR-2218 and SLGN through Week 36 for Cohort 1 and Cohort 2 Group A
- Discontinued all study treatment for Cohort 2 Group B participants
- Stopped all sample collections related to nivolumab
- NUC treatment cessation was no longer required for NUC treated participants (Cohort 1)

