1.3. Sample Size and Power

2. TYPE OF PLANNED ANALYSIS

2.1. Primary Analysis

The Primary Analysis will be conducted after all participants have completed FU Week 24 or early terminated from the study prior to FU Week 24.

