4. PARTICIPANT DISPOSITION

4.1. Participant Enrollment and Disposition

Key study dates (ie, first participant screened, first participant enrolled, last participant last visit for the primary endpoint, and last participant last visit for the clinical study report) will be provided.

A summary of participant enrollment will be provided by cohort for each country or region, investigator within a country or region, and study overall. Within Cohort 2, the summary will be presented by treatment group (Group A or Group B) and stratification group (HBsAg \geq 3 or HBsAg \leq 3 log₁₀ IU/mL). The summary will present the number and percentage of participants enrolled/randomized. For each column, the denominator for the percentage calculation will be the total number of participants analyzed for that column. For Cohort 2, if there are discrepancies in the value used for stratification assignment between the IXRS and the clinical database, the value collected in the clinical database will be used for the summary. A listing of participants with discrepancies in the value used for stratification assignment between the IXRS and the clinical database at the time of data finalization will be provided.

The randomization schedule used for Cohort 2 will be provided as an appendix to the CSR.

A summary of participant disposition will be provided by cohort and study overall. Within Cohort 2, the summary will be presented by treatment group (Group A or Group B) and stratification group (HBsAg \geq 3 or HBsAg \leq 3 log₁₀ IU/mL). This summary will present the number of participants screened, the number of participants who met all eligibility criteria but were not enrolled/randomized with reasons participants not enrolled/randomized, and the number of participants in each of the categories listed below:

- All Enrolled Analysis Set
- All Randomized Analysis Set
- Full Analysis Set
- Safety Analysis Set
- FU Analysis Set
- SLGN PK Analysis Set
- SLGN PK Substudy Analysis Set
- SLGN completion status
 - Completed SLGN
 - Prematurely discontinued SLGN

- Reasons for premature discontinuation of SLGN
- Nivolumab completion status
 - Nivolumab not initiated
 - Completed nivolumab
 - Prematurely discontinued nivolumab
- Reasons for premature discontinuation of nivolumab
- VIR-2218 completion status
 - Completed VIR-2218
 - Prematurely discontinued VIR-2218
- Reasons for premature discontinuation of VIR-2218
- TAF completion status (for Cohort 1 during treatment phase only)

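### Section 6.1.3 lets the primary efficacy analysis go ahead once participants have stopped study drug, whereas Sections 1 and 2.1 require them to have left the study

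*SAP*

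**What the plan says.** Three places in the SAP time the same analysis.

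- Section 1 places the Primary Analysis "when all participants complete Follow-Up (FU) Week 24 or early terminated from the study prior to FU Week 24".
- Section 2.1 places it "after all participants have completed FU Week 24 or early terminated from the study prior to FU Week 24".
- Section 6.1.3, on the primary endpoint in the Full Analysis Set, places it "after the last participant has completed FU Week 24 assessments or prematurely discontinued study drug".

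Section 1.2.1 describes what happened to treatment. Enrolment was complete, and "all participants were undergoing study treatment when the decision was made to stop nivolumab administration". The sponsor then took these measures, among others: "Stopped further nivolumab administration for all study participants across all cohorts"; "Discontinued all study treatment for Cohort 2 Group B participants"; and "Continued treatment with VIR-2218 and SLGN through Week 36 for Cohort 1 and Cohort 2 Group A".

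The SAP treats stopping drug and leaving the study as separate events. Section 4.1 tabulates completion status for each drug (including "Prematurely discontinued nivolumab"), for follow-up and for the study. The FU Analysis Set in Section 3.1.5 includes people who stopped drug early and then had a follow-up visit.

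**The concern.** The primary endpoint is functional cure at FU Week 24. A participant who stops drug has only begun the 24 weeks that lead to it. Section 6.1.3 nevertheless treats that participant as someone the analysis no longer has to wait for. Sections 1 and 2.1 release the analysis only from participants who can no longer supply the result.

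In many trials this slip would touch a handful of people. Here the sponsor stopped one drug in every cohort and all drugs in one group, so the condition in 6.1.3 may describe a large share of participants. A cut taken under it could include people whose FU Week 24 sample is still to come. They would stay in the Full Analysis Set denominator, and a missing result might be scored as failure.

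**Working it through.** **1. The conditions side by side.** The first limb, completing FU Week 24, is the same in all three sections. The second limb is leaving the study before FU Week 24 in Sections 1 and 2.1, and stopping study drug in Section 6.1.3. Section 3.8.2 counts FU Day from the composite last on-treatment date, so stopping all the drugs that define that date starts the follow-up clock. The two second limbs are different events.

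**2. Two readings of study drug.** Section 6.1.3 does not say whether it means any one drug or all of them.

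- *Any one drug.* Cohort 1 and Group A participants whose nivolumab was cut short meet the limb while still taking other study drugs. Those who had completed nivolumab, or never started it (a separate category in Section 4.1), do not meet it that way.
- *All drugs.* Group B participants still on treatment meet it at the stop. In Cohort 1 and Group A, only those who stopped everything early meet it.

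**3. How early the limb can be met in Cohort 1 and Group A (any-drug reading).** The inputs are the planned schedule in Section 1.2, the study days in Table 3-1, the on-treatment rules in Section 3.8.2 and the FU Week 24 window in Table 3-10 (nominal FU Day 169, limits 128 and 211).

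- Last SLGN dose: 24 weekly doses from study day 85, so 85 + 7 × 23 = day 246.
- Last on-treatment date for SLGN: 246 + 7 − 1 = day 252. This is later than VIR-2218 (141 + 28 − 1 = 168) and than nivolumab last given at Week 28 (197 + 28 − 1 = 224), so it sets the composite date.
- Nominal FU Week 24: 252 + 169 = day 421, with window days 252 + 128 = 380 to 252 + 211 = 463.
- The SAP does not give the dates of the last nivolumab doses. Assume a range from Week 12 (day 85) to Week 28 (day 197). Nominal FU Week 24 then falls 421 − 85 = 336 to 421 − 197 = 224 days after the last nivolumab dose.

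**4. Group B.** FU Week 24 counted from last dose:

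| Drug setting the composite date | Nominal | Window closes |
|---|---|---|
| SLGN (last dose + 6) | 6 + 169 = 175 days | 6 + 211 = 217 days |
| Nivolumab (last dose + 27) | 27 + 169 = 196 days | 27 + 211 = 238 days |

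The SAP rests on protocol amendment 2, dated 12 April 2023, and the note to Figure 1-1 says the rationale for the stop is in the protocol. Assume from this that the stop came no later than that date. Even with a last Group B dose on 12 April 2023, day 238 is 6 December 2023. The SAP was signed on 18 and 19 April 2024 and is to be finalized before the Primary Analysis.

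**5. What one misclassified participant is worth.** Counting as a failure someone who would have been cured moves a planned group of 40 by 1/40 = 2.5 percentage points and a planned group of 20 by 1/20 = 5 points. These are ceilings per participant. The SAP gives no cure rate from which to estimate an expected bias.

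**The case against.** The best defence is that this is a drafting slip with little practical reach, and much of that stands.

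- Section 2 is the part of the SAP that defines the planned analyses. Section 1 agrees with it, and a programmer would probably follow them. That makes a wrong cut less likely but leaves the contradiction in the section that governs the primary endpoint.
- The trigger concerns the last participant in the whole study. On the all-drugs reading, Cohort 1 and Group A participants who complete treatment hold the analysis until their own FU Week 24. On the any-drug reading, anyone who completed nivolumab or never started it does the same. Those not yet at Week 12 when nivolumab stopped were, by schedule, among the furthest from FU Week 24, so waiting for them would cover many others. The SAP does not say how many there were.
- The nonevent rule is written in Section 6.2.2 among the serology definitions. Section 6.1.3 states no rule of its own, and Section 3.6.1 says missing data are generally not imputed. Scoring a pending result as failure, for HBV DNA as well as HBsAg, is an inference.
- No hypothesis is tested, and a Final Analysis follows once all participants have finished.

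A reader might also infer that Group B, having lost all treatment, would be cut before its FU Week 24 data existed and so be biased downward. The documents do not support this. Group B stopped while the other groups continued, so at a single cut it would generally be further into follow-up. On the dating above, its last window had closed before the SAP was signed. Pending results are more plausible in Cohort 1 or Group A.

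**Conclusion.** Wrong as written, minor severity. Section 6.1.3 contradicts Sections 1 and 2.1, and its condition does not fit an endpoint measured 24 weeks into follow-up. That follows from the text alone.

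The practical reach depends on the meaning of study drug. On the any-drug reading, the limb could be met 224 to 336 days before nominal FU Week 24 by many in Cohort 1 and Group A, given the assumed range of last nivolumab doses and the planned schedule. On the all-drugs reading, it leaves unprotected only those who stopped everything early and remain in follow-up. Harm to the estimate further requires that the cut actually be taken under 6.1.3 and that the serology nonevent rule be extended to the primary endpoint. Neither the direction nor the size of any effect on Group A minus Group B can be established from the SAP. The conclusion that Group B is probably safe rests on the stop predating amendment 2.

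**What to change.** In Section 6.1.3, replace the limb about stopping study drug with the Section 2.1 condition, so that the analysis is performed "after all participants have completed FU Week 24 or early terminated from the study prior to FU Week 24". All three sections then state one rule, and the any-drug or all-drugs question no longer arises for timing. The cost is one phrase in the SAP or, since the SAP is already signed, a recorded clarification in the clinical study report, where Section 1 says later changes are documented. No data collection, method or planned estimate changes.
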